15. WITHDRAWAL OF PARTICIPANTS	20
16. DATA MANAGEMENT AND CONFIDENTIALITY	20
16.1 Project Data Collection	20
16.2 Data Storage and Maintenance	20
16.3 Confidentiality	20
17. Provisions to Protect the Privacy Interests of Participants	21
18. SHARING OF RESULTS	21
19. DATA AND SPECIMEN BANKING	21

20. STUDY ANALYSIS	21
20.1 Statistical Hypothesis	21
20.2 Sample Size Justification	22
20.3 Statistical Methods	22
21. POTENTIAL BENEFITS TO PARTICIPANTS	22
22. RISKS TO PARTICIPANTS	23
23. PROVISIONS TO MONITOR THE DATA TO ENSURE THE SAFETY OF THE PARTICIPANTS	23
24. ECONOMIC BURDEN TO PARTICIPANTS	23
25. RESOURCES AVAILABLE	23
26. MULTI-SITE RESEARCH	24
27. REFERENCES	24
28. APPENDICES	26

STATEMENT OF COMPLIANCE

I confirm that I have read this protocol. I will comply with the IRB-approved protocol, and applicable regulations, guidelines, laws, and institutional policies.

I agree to ensure that all staff members involved in the conduct of this study are informed about their obligations in meeting the above commitment.

Name	Signature	Date
Name	Signature	Date
[name]		08/08/23

[name]
Principal Investigator

SYNOPSIS

Study Title	Community Health Outreach to Increase Cervical Cancer Education and Self-Collection Screening (CHOICES) Program for Southeast Asian Immigrant and Refugee Women in Wisconsin
Brief Summary	The primary purpose of this study is to determine whether educational workshops paired with self-collected high-risk human papillomaviruses (hrHPV) screening will increase participation in cervical cancer screening among Southeast Asian refugee and immigrant populations in Wisconsin compared with offering clinician-collected screening (total sample size: 250 participants). We hypothesize that participation in cervical cancer screening will be higher among women in the intervention group as compared to the control group.
Number of study sites	1
Study Design	Workshops are randomized to either a control or intervention group.
Primary Objective	To evaluate whether educational workshops paired with self-collected hrHPV screening will increase participation in cervical cancer screening among Southeast Asian refugee and immigrant populations in Wisconsin compared with offering clinician-collected screening.
Secondary Objective(s)	To evaluate participant satisfaction with the educational workshops using satisfaction surveys.
Research Intervention(s)	Control workshops are workshops where participants are provided education on standard-of-care for cervical cancer screening such as pap smear and HPV testing through clinician-collection methods using speculum and cervical swabs. Intervention workshops are workshops where participants are provided all the same education as control as well as additional education on self-collection for HPV-only testing using vaginal swab as an additional method. After each workshop, each group will be offered to participate in their assigned group's screening method (clinician-collected or self-collected).
Device used on study (including any IND/IDE #)	Evalyn® Brush (Rovers® Medical Devices, Netherlands) Regulation Number# 884.4530 Roche Cobas4800 HPV Test System (Roche Molecular Systems Inc., Rotkreuz, Switzerland)
Study Population	Southeast Asian Immigrant and Refugee (Karen, Karen, Burmese, and Hmong) Women in Wisconsin, aged 25-65, eligible for cervical cancer screening.
Sample Size	240
Study Duration for individual participants	Subject participation is limited to the workshop session, post-workshop cervical cancer screening, and follow-up contact on results of screening tests.
Study Specific Abbreviations/ Definitions	ASCCP, Society for Colposcopy and Cervical Pathology; CHW, community health worker; FDA, Food and Drug Administration; HCP, health care provider; hrHPV, high-risk human papillomaviruses; LMP, last menstrual period; MCHH Milwaukee Consortium for Hmong Health; ROI, release of information

1. INTRODUCTION

1.1 Background

Despite effective screening and early treatment options, 311,000 women die of cervical cancer worldwide every year.¹ In the United States, Hmong-American immigrant women experience incidence and mortality rates four times those of their non-Latina white counterparts and have alarmingly low participation in cervical cancer screening.² With the third highest Hmong population in the US, Wisconsin's minority communities face similar health disparities.¹ Factors such as modesty, fatalism, lack of knowledge, and lack of access impede participation in screening and treatment for cervical cancer. These barriers can be attributed to cultural beliefs, patriarchal family/clan structure, language barriers, and mistrust or lack of experience in the Western medical system.^{3,4}

In women 25 and over, screening for cervical cancer screening through testing for high-risk human papillomaviruses (hrHPV) has been found to be more sensitive than cytology and effective in preventing cervical cancer.⁵ **Self-collection** has been a proposed strategy to reach under-screened women worldwide. Recent systematic reviews and meta-analyses have shown that offering hrHPV self-collection at home to non-attendees can significantly increase attendance and the detection of high-grade cervical lesions, compared to currently widely-used reminder letters for clinician-based screening.^{6,7} Most studies have found at least a doubled response rate to submitting a self-sample versus scheduling an on-site pap smear, even among under-screened populations.⁸⁻¹⁰ Furthermore, with improved hrHPV polymerase chain reaction (PCR)-based testing technology, the sensitivity for detection of human papillomavirus (HPV) infections is comparable in most self-collect samples when compared to clinician-collected samples. Kaiser Permanente ran a similar study across 20,000 women who were behind on their screening and found that 50% more women chose to return a self-sample than schedule an in-office screen. A large population-based cervical cancer self-collected study in Argentina found that HPV-based screening doubles the detection rate ratio (DRR) for HPV screening.⁹ These studies have led some countries, such as Australia, to institute a self-collection option nationally.^{8,10} Furthermore, our previous work in rural Zimbabwe found that community-based screening using self-collected samples increased participation in cervical cancer screening from a baseline of 5% to 82% participation.¹¹⁻¹³ As part of a comprehensive cervical cancer screening program, the utilization of self-collected samples has advantages from both a public health and individual participant perspective. Some of the barriers to screening can be mitigated by self-collection, and resources can be better allocated to participants at the highest risk of developing cervical cancer.

1.2 Rationale

The effectiveness of offering self-collection sampling options to Southeast Asian refugee and immigrant populations to improve cervical cancer screening participation has not been investigated. The Milwaukee Consortium for Hmong Health (MCHH), supported by the Well Woman Program, has had success increasing participation in breast cancer screening through outreach and education activities. However, it continues to have **limited success** engaging women in cervical cancer screening. We have established a partnership with MCHH to develop innovative cervical cancer workshops that combine community health worker (CHW)-led engagement with self-collected hrHPV screening, with the primary objective of increasing participation, awareness, and engagement in cervical cancer screening and treatment activities among this population.

2. STUDY OBJECTIVES AND ENDPOINTS

Objectives	Endpoints

Primary
 
 To evaluate whether educational workshops paired with self-collected hrHPV screening will increase participation in cervical cancer screening among Southeast Asian (Hmong, Burmese, Karen, and Karen) refugee and immigrant populations in Wisconsin compared with offering clinician-collected screening. 	
 Uptake of cervical cancer screening using a self-collect device vs. clinician-based screening.

Secondary
 
 To evaluate participant satisfaction with the educational workshops using satisfaction surveys. To evaluate participant willingness to use self-collection as method for screening. 	
 Participant satisfaction as determined using qualitative methods. General willingness to use a HPV self-collect device at home and/or as the preferred collection method for cervical cancer screening, assessed via mixed methods survey.

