We anticipate a total of thirty workshops, fifteen of which will be control and fifteen of which will be intervention, will be planned in total over a sixteen-month period (Table 1). All workshops will have 8 participants recruited due to limited space of the community center, time, and to accommodate physical spacing needs. There will be two workshop sessions per day (one in the morning and one in the afternoon).

Table 1. Planned Number of Hmong and Karen Participants in the Intervention and Control Workshops

Intervention Workshop	1	2	3	4	5	Total
Hmong	8	8	8	8	8	40
Karen	8	8	8	8		36
Karen	8	8	8			24
Burmese	8	8	8			24
Control Workshop						
Hmong	8	8	8	8	8	40
Karen	8	8	8	8		36
Karen	8	8	8			24
Burmese	8	8	8			24

[figure not shown]
After workshop conclusion, participants will be offered same-day on-site cervical cancer screening depending on assignment in the control or intervention group (clinician-collected screening or self-collection screening, respectively). Participants, regardless of engagement in screening, will then complete a post-evaluation workshop survey (consisting of two surveys, see Appendix C).

Due to ethical concerns and our hypothesis that this population is less likely to do cervical cancer screening if offered clinician-collected screening only. Participants in the control workshops who answer “yes” on the survey to the question “If given the option, instead of having a clinician collect the sample, would you want to collect the sample on your own?,” will be subsequently offered self-collection for their screening method. CHWs will provide to these participants a 5-minute 1-on-1 instruction tutorial on self-collection, translated handout, private room to collect a sample, and then samples sent to the laboratory per protocol.

Similarly, participants will be made aware during the education of the self-collection method, that this is not a usual method that is offered in many clinical practices. If a participant were to visit their usual primary care doctor for an exam, a pelvic examination to obtain a clinician-collected cervical swab for HPV testing and pap smear is the usual method which they should anticipate. We are offering self-collection as studies show growing validity of HPV self-sampling, particularly among hard-to-reach populations.¹⁴⁻¹⁸ With this understanding, self-collection will be offered and encouraged although if participants desire clinician-collection instead this is option will also be made available.

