13.1.4 Post-Workshop Sample Collection

Immediately after workshops, participants will be offered same-day opportunity to engage in cervical cancer screening either through clinician collection (if in the control) or self-collection (if in the intervention group). Participants who do not desire screening through the program will be encouraged to attend cervical cancer screening with their local health department or provider.

Pregnant women will be excluded from this study if they are known to be pregnant at the time of screening, although additional measures will be taken prior to sample collection for women unaware of pregnancy status. All participants will be asked the date of their last menstrual period (LMP). Participants will be requested to provide a urine sample for on-site urine pregnancy testing if more than six weeks from LMP unless post-menopausal or meeting criteria of relative certainty a woman is not pregnant. CDC 2016 Selective Practice Recommendations for reasonable certainty states, a health care provider can be reasonably certain that women is not pregnant if she has no symptoms or signs of pregnancy and meets any one of the following criteria:

- is ≤7 days after the start of normal menses
- has not had sexual intercourse since the start of last normal menses
- has been correctly and consistently using a reliable method of contraception
- is ≤7 days after spontaneous or induced abortion
- is within 4 weeks postpartum
- is fully or nearly fully breastfeeding (exclusively breastfeeding or the vast majority [≥85%] of feeds are breastfeeds), amenorrheic, and <6 months postpartum¹⁴

Results of the urine pregnancy test will be provided immediately to the participant and if positive, excluded from the remaining of the study although still counted as a participant. Due the possibility that participants who are pregnant and included in the study (educational workshops only, will not be included in either screening method—clinician-collected or self-collection). For risks involved with the educational workshop portion of the study:

- The research involves no more than minimal risk to pregnant women and fetuses.
- The research holds prospect of direct benefit to the pregnant women, the prospect of direct benefit both to the pregnant woman and the fetus, or no prospect of benefit for the woman nor the fetus.

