14. COMPARISON OF USUAL CARE AND STUDY PROCEDURES

Standard of care for women recommended by the ASCCP is screening for cervical cancer starting at age 21 with pap smear every three years and then co-testing (HPV and pap smear) starting at age 30. American Cancer Society (ACS) recommends screening starting at age 25 with primarily HPV only every five years. Both societies recommend for screening to continue until age 65 unless history of abnormal results or hysterectomy unrelated to cervical dysplasia.

These research procedures follow standard of care as expected for care delivered to participant population at UW-Madison/UW Health, regarding clinician collection of samples for cervical cancer screening. In both the intervention and control arms of the study, participants will be offered the opportunity for cervical cancer screening via a licensed health care professional. The intervention is education and use of self-collection for HPV only testing using vaginal swab as an additional method to usual care, i.e., pap smear and HPV testing through clinician-collection methods using speculum and cervical swabs (control).

Overall, research has shown self-collection HPV testing as an acceptable method for screening especially in hard-to-reach populations, although concerns remain on potential for false negative results.¹⁵⁻¹⁹ Participants will be informed of this risk and encouraged if opting for self-collection through this method to follow-up with their primary care physician for additional screening per recommended guidelines. Reporting of results will further specify this comparison to standard procedure (outlined in section 13.1.5.3 Reporting of Results).

Otherwise follow up recommendations based on results for clinician-collection (outlined in section 13.1.5 Follow up on Results) is also standard of care, and there will be no delay in care or treatment as a result of being in this study.

If patients have a primary care clinic, their results will not automatically flow into their electronic health record. If an ROI for the PCP has been filled out (see section 13.1.1 and 13.1.3), copy of the results and recommendation for next steps will be provided for continuity of care. Participants will also receive a paper copy of their results to maintain for their own records.

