20.3 Statistical Methods

20.3.1 Primary Outcome Measures and Analysis:

The primary outcome measure is uptake of cervical cancer screening. The results will be reported through summary statistics of the number of participants in each group subsequently engaging or seeking out cervical cancer screening either through services offered after workshop education or self-reported desire to follow up through their community health care provider. Comparisons between the study arms will be based on a binomial test. The analysis will indicate if participants offered additional self-collection education would be more willing to engage in cervical cancer screening. Summary statistics will also include uptake of screening differentiated by reported ethnicity.

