Section C (continued)

In the workshop you attended today, we did not discuss self-collection as an option.

If self-collection was an option, would you have preferred this method?

Yes

Maybe

No

→ Any remaining questions you have about the workshops or about cervical cancer? **Survey End**

At this time - please provide a quick 1 on 1 instruction on self-collection for cervical cancer screening.

After the participant is done, please return to complete the remainder of this survey.

Patient agreed and collected a self sample → Skips to to Section E

Patient declined a self sample today

→ Any remaining questions you have about the workshops or about cervical cancer? **Survey End**

Section D

Did the participant get screening for cervical cancer today? (Self Collected)

Yes, clinician collection → Skips to to Section F

Yes, self-collection → Skips to to Section E

No → Skips to to Section G

Section F

How comfortable did you feel with this method?

Extremely comfortable

Somewhat comfortable

Neither comfortable nor uncomfortable

Somewhat uncomfortable

Extremely uncomfortable

How likely would you get screening for cervical cancer again?

Extremely likely

Somewhat likely

Neither likely nor unlikely

Somewhat unlikely

Extremely unlikely

Any remaining questions you have about the workshops or about cervical cancer?

Survey End

Section E

How comfortable did you feel with this method?

- Extremely uncomfortable
- Somewhat uncomfortable
- Neither comfortable nor uncomfortable
- Somewhat comfortable
- Extremely comfortable

How likely would you do self-collection for cervical cancer screening again?

- Extremely unlikely
- Somewhat unlikely
- Neither likely nor unlikely
- Somewhat likely
- Extremely likely

Would you have preferred a clinician to help with the collection?

- Do not prefer
- Prefer slightly
- Prefer a moderate amount
- Prefer a lot
- Prefer a great deal

Did you have any confusion with the instructions?

- No
- Yes

How likely are you to recommend this method to others?

- Extremely unlikely
- Somewhat unlikely
- Neither likely nor unlikely
- Somewhat likely
- Extremely likely

Any remaining questions you have about the workshops or about cervical cancer?

Survey End

Section G

Will you get screening for cervical cancer in the near future (within the next year)?

- Yes
- Maybe
- No

Do you have any concerns with getting screening for cervical cancer?

Where would you go to get cervical cancer screening?

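### Section 2 words the primary endpoint by collection device while Section 20.3.1 counts any uptake by arm; intervention women who choose clinician collection are scored differently under the two wordings

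*Combined protocol and SAP*

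**What the plan says.** **The endpoint.** The table in Section 2 words the primary endpoint as "Uptake of cervical cancer screening using a self-collect device vs. clinician-based screening". The objective in the same row names no method for the outcome: it asks whether the workshops "will increase participation in cervical cancer screening among Southeast Asian (Hmong, Burmese, Karen, and Karen) refugee and immigrant populations". Section 20.1 states the hypothesis as higher participation in the intervention group. Section 20.3.1 says "The primary outcome measure is uptake of cervical cancer screening". It counts women in each group who engage "either through services offered after workshop education" or who report a wish to follow up with their own provider, and it compares the study arms.

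**The offer.** Section 13.1.4 describes the same-day offer as "either through clinician collection (if in the control) or self-collection (if in the intervention group". Other places widen it for the intervention arm:
- Section 11 says that self-collection is encouraged, but "if participants desire clinician-collection instead this is option will also be made available".
- Section 14 says that in both arms "participants will be offered the opportunity for cervical cancer screening via a licensed health care professional".
- Section 9 says that a woman who declines the method offered is then offered the other one.
- Appendix C, Section D, which is the survey branch for intervention workshops, has a separate answer "Yes, clinician collection".

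The plan therefore expects some intervention women to be screened by a clinician. No sentence says how they count in the primary outcome.

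**The concern.** Take an intervention woman who hears about self-collection and then has a clinician sample the same day. Under 20.3.1 she has taken up screening and is a success. Under the literal Section 2 wording she did not use a self-collect device, so she is either a failure or belongs with clinician-based screening. The primary count in the intervention arm then depends on which section the analyst follows, and that choice could be made after the data are seen.

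The device wording also fits the design poorly. Workshops are randomised. One arm gets education on, and access to, clinician collection; the other gets the same with self-collection added. A comparison by device used would not be a comparison of randomised groups. It would also lack a natural denominator, because a woman who declines screening has used neither device.

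**Working it through.** **1. Inputs.** Section 20.2 gives 125 women per arm, a one-sided 0.05 binomial test, and control rates of 0.61, 0.71 and 0.81. The detectable intervention rates at 0.80 power are 0.77, 0.85 and 0.93. All calculations below treat women as independent, as the plan does.

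**2. The plan's own figures.** The form of binomial test is not specified. I used the exact power of the one-sided Fisher test, summed over both binomial distributions:

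power = Σ Σ b(x0; 125, p0) · b(x1; 125, p1) · 1[p_F(x0, x1) ≤ 0.05],

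where p_F = P(H ≥ x1) and H is hypergeometric with 250 women, x0 + x1 screened and 125 drawn. For 0.81 v 0.93 this gives 0.854, against the stated 0.85. All nine table entries are the smallest two-decimal rate at which this power reaches its target. The stated power figures are sound.

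**3. How many women change the result.** Set the observed counts at the planned rates (125 × rate, rounded). Then recount k intervention women from success to failure and recompute the one-sided Fisher p-value.

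| Control v intervention | Screened | p, all counted | k at which p first exceeds 0.05 | p at that k |
|---|---|---|---|---|
| 0.61 v 0.77 | 76 v 96 | 0.005 | 7 | 0.054 |
| 0.71 v 0.85 | 89 v 106 | 0.007 | 5 | 0.051 |
| 0.81 v 0.93 | 101 v 116 | 0.004 | 5 | 0.056 |

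Five of 125 is 4.0% of the arm and seven of 125 is 5.6%. With a pooled z test the tipping points are one woman higher in each row: 8, 6 and 6.

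**4. Power if clinician choosers count as failures.** Let s be the share of screened intervention women who choose the clinician. The documents do not give s; 5%, 10% and 20% are assumptions. The counted rate is p1 × (1 − s). For p1 = 0.93 this is 0.93 × 0.95 = 0.884, 0.93 × 0.90 = 0.837 and 0.93 × 0.80 = 0.744.

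| Control v true intervention | s = 0 | s = 5% | s = 10% | s = 20% |
|---|---|---|---|---|
| 0.61 v 0.77 | 0.84 | 0.61 | 0.35 | 0.05 |
| 0.71 v 0.85 | 0.82 | 0.51 | 0.21 | 0.01 |
| 0.81 v 0.93 | 0.85 | 0.42 | 0.11 | 0.001 |

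At s = 0 the two readings agree on these women. I did not compute the variant that moves them to the comparator side, because the documents give no denominator for it.

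**5. Sample size.** The synopsis table gives 240 participants. At 120 per arm the pattern is the same: for 0.61 v 0.77, power is 0.82 with all counted and 0.51 if 5% of the arm is recounted as failures.

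**The case against.** The strongest reply is that the device reading is weak and that Section 2 is shorthand for the two arms. Much of this stands. The objective in the same table row is about participation. Section 8 says that uptake will be compared between the two groups, Section 20.1 compares the groups, and 20.3.1, the only section on the primary analysis, compares arms without naming a method. Sections 11, 13.1.2 and 14 already present self-collection as an added option. The steep falls in power need an analyst to score a screened woman as unscreened, against 20.3.1, and they rest on an assumed share.

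A reader might infer that the trial plans to compare devices and so gives up its randomisation. The documents do not support that: no passage plans an analysis by method received, and none calls a clinician-screened intervention woman a failure. A reader might also infer that the clinician option always comes at the same moment as self-collection. Section 11 can be read that way, but Section 9 places the other method after a refusal.

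What remains is the conflict itself. The section that defines the endpoint says something different from the section that analyses it. The device reading also has some support elsewhere: the debriefing text in Section 11 says information was withheld in order to measure participation in self-swab.

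**Conclusion.** The inconsistency is real, and a sensible default exists: count intervention women screened by either method as successes and compare by arm. Taken literally, Section 2 would score some of them otherwise, and no passage says which section prevails. In the protocol's own scenarios, recounting 5 to 7 of 125 intervention women removes significance. This rests on observed rates equal to the planned ones, a one-sided Fisher test and independent women. It is not a forecast, because the number who will choose the clinician is not stated.

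It would go too far to say that the plan has no workable primary endpoint, that its power figures are wrong or that power will be lost. Under 20.3.1, clinician choosers count as uptake and the planned comparison is unaffected by them.

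**What to change.** State one identical primary endpoint in Sections 2 and 20.3.1: a same-day on-site screening sample, compared by randomised workshop arm.

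- **Intervention arm:** count a sample by either method, whether the woman chose the clinician directly or after declining self-collection.
- **Control arm:** count a clinician-collected sample obtained before the post-survey self-collection offer. That later offer delivers the intervention's extra option to control women, so samples from it are reported separately.
- **Intention:** take the self-reported wish to follow up out of the primary count and report it separately. Changing Section 2 alone would leave 20.3.1 with a conflicting definition.
- **Method:** give the split between self-collection and clinician collection within the intervention arm descriptively.
- **Contrast:** in Sections 2, 13.1.4 and 20.2, describe it as clinician collection plus the option of self-collection versus clinician collection.
- **Timing:** Sections 9, 11 and 13.1.4 differ on when the other method is offered and must be reconciled.

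The cost is mainly wording. The claim becomes slightly narrower (the effect of adding an option), and the primary count loses its intention component. Section 16.2 already lists type of screening done among the REDCap items. It does not list which offer the sample followed, so recording that would remove doubt.
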